#### *Week 4 Visit/End of Study*

Participants will be asked to complete a 3-day bladder diary during the week preceding their week 4 visit. At their week 4 visit, participants will complete the PGI-I, UDI-6, IIQ-7, and FSFI questionnaires, as well as the Interval Study Questionnaire. All participants will undergo a pelvic exam to assess for any potential adverse events, such as vaginal abrasions, lacerations, or infections. This will complete the active portion of study participation.

**Table 1: Study Assessments by Visit**

Evaluation	Baseline	Week 0	Week 2	Week 4
Consent	X			
Demographics	X			
Device Fitting		X	X	
MESA	X			
3-day bladder diary	X			X
UDI-6	X			X
IIQ-7	X			X
FSFI	X			X
Interval Study Questionnaire			X	X
PGI-I				X

At the end of the visit the participant will be given information about the device they were not randomized to use. Participants that were randomized to the continence pessary will be given information on the Poise Impressa® and information on where they can purchase these devices as this would be routine in an office practice. Participants that were randomized to the Poise Impressa® arm can have a pessary fitting scheduled with a provider as part of routine care.

Participants can choose to pursue other options, such as surgery or pelvic floor physical therapy after completion of the study or if they choose to drop out. Participants that desire potential surgery will be scheduled with a physician for further discussion of their options.

This visit is outside of the study and will be considered to be a routine follow up visit.

#### **Month 6 Phone Call**

The research assistant will call each participant 6 months after their week 0 visit (+/- 30 days) for a follow-up. During this call, participants will verbally complete the follow-up questionnaire as well as the PGI-I.

#### **Participant Cost**

There will be no out of pocket costs to the participant to participate in this study. The initial visit to the office is billed to the insurance company as this is a visit that is scheduled by the participant for a visit to address one or more of their pelvic floor disorders. Participants interested in non-surgical management of SUI are identified and offered enrollment if they meet all necessary criteria. Patients would receive a continence pessary as part of routine care if they were not enrolled in the study. Participants that are randomized to the continence pessary arm will have their insurance charged as part of standard of care for the device, intervention visit, week 2 visit, and any unscheduled visits. As week 4 is considered a study visit, they will not be charged for this visit. Participants that are randomized to the Poise Impressa® arm will have their devices provided free of cost, along with their study visits (intervention visit, week 2, and week 4) since it is not standard of care to provide these devices or have follow up visit as patients are able to purchase these over-the-counter without physician guidance. Any unscheduled visits due to an adverse event will be considered a billable visit since a patient would come to the office for this problem if they were using this device outside of the study.

#### **Participant Incentive**

All participants will receive \$10 upon study completion.

#### **Statistical Analysis**

##### **Randomization**

Participants will be randomized to either continence pessary or Poise Impressa® in a 1:1 ratio through random permuted blocks of 4 and 6 stratified by institution. Randomization will be conducted via REDCap to ensure proper randomization and to aid in allocation concealment.

#### **Sample Size Estimate**

We aim to detect a clinically significant difference of 50% improvement with continence pessary versus 25% with the Poise Impressa®. Assuming an 80% power, an alpha error of 5% and a 20% dropout rate we need 138 participants total (69 per group) to detect this difference. We plan to assess for differences in secondary outcomes between arms while acknowledging that we may be underpowered to detect significant differences in these outcomes.

#### **Statistical Analysis**

De-identified data from the study database will be analyzed. Continuous variables will be analyzed by students t-test and categorical variables will be analyzed by chi-square or Fischer's exact tests. A regression analysis will be performed for both continuous and discrete outcomes in order to simultaneously adjust for baseline demographics and characteristics in addition to treatment effects. A p-value of less than 0.05 will define statistical significance and 95% confidence intervals will be documented. Our primary outcome, SUI treatment success as assessed by PGI-I score, will be analyzed by an intention-to-treat. A per-protocol analysis will also be performed as a planned secondary assessment of the primary outcome. All statistical analysis will be performed using SPSS. Data will be presented according to CONSORT 2010 guidelines for randomized controlled trials(15).

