**Secondary outcomes:**

**Quality of life (QoL):** Participants' QoL will be assessed with the following three validated questionnaires:

1. Urogenital Distress Inventory (UDI-6)(9, 12): This short form 6-item questionnaire measures urinary incontinence symptom bother.
2. Urinary Incontinence Impact Questionnaire (IIQ-7)(9, 12): This short form 7-item questionnaire measures the functional impact of urinary incontinence.
3. Female Sexual Function Index (FSFI)(13): This 19-item questionnaire is used to assess sexual functioning in women.

These questionnaires will be completed by participants at baseline and then again at the end of the 4-week study period. A change score will be calculated by subtracting the two scores.

**Interval Study Questionnaire:** Participants will complete this questionnaire at weeks 2 and 4. It consists of questions addressing menstrual status, device use, adverse events, and Likert scale questions assessing *device satisfaction, ease of use, comfort, and likelihood of continued use*. The questions will consist of the following:

- "Did you have your period during the last 2 weeks?"
  - If yes, "During the last two weeks, how many days were you on your period?" and "During the last two weeks, how many days did you wear your device?"
- "On average, how many hours a day did you wear your device?"
- "How satisfied were you with the device?" Participants may respond with "completely satisfied," "somewhat satisfied," or "not at all satisfied," "(14)." Responses include "completely comfortable," "somewhat comfortable," "not at all comfortable."
- "In general, how comfortable is the device?" Responses include "completely comfortable," "somewhat comfortable," "not at all comfortable."
- Ease of use will be assessed by asking "how easy/difficult was the device to use?", "how easy/difficulty was the device to insert?" and "how easy/difficult was the device to remove?" Responses will include "very easy," "easy," "somewhat easy," "somewhat difficult," "difficult," "very difficult."
- Likelihood of continued use will be assessed using the same Likert scale ranging from "strongly disagree" to "strongly agree" and asking participants to rate their level of agreement with the statement "I would continue to use this device in the future."

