**Figure 1. Study Flow Chart**

#### *Baseline Visit*

Patients who are interested in the study will be consented and screened for inclusion/exclusion criteria. If there is concern for a urinary tract infection or vaginal infection, as previously defined in the exclusion criteria, further baseline data collection will be deferred until evaluation and treatment has been completed.

Participants will complete a demographics questionnaire and their medical and surgical history will be abstracted from electronic medical records. POP-Qs completed within the last year may be used to confirm study criteria; otherwise a new POP-Q must be completed. Participants will complete the MESA, UDI-6, IIQ-7, and FSFI questionnaires, and will then be randomized to an intervention group. Participants will be scheduled for their week 0 fitting visit, and then sent home with instructions to complete a 3-day bladder diary.

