## Baseline Characteristics

Baseline characteristics will be assessed using descriptive univariate analyses to characterize the total study population. Histograms will be generated to characterize the distribution of the specific outcome being assessed. The baseline characteristics of the two study arms will be analyzed using the Student's t test for continuous variables, and Chi-Square or Fisher's exact tests for categorical variables. Although a comparison of the baseline characteristics between study arms is not necessarily needed given the randomized design, this is a study of 150 people and so we have planned to include a regression analysis.

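### The tests named for UDI-6, IIQ-7 and FSFI use baseline only by subtraction, no named test uses the institution strata, and the planned regression names neither term and is not ranked against the simple tests

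*Combined protocol and SAP*

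**What the plan says.** All places are in the combined protocol and SAP.

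- **Baseline Visit:** "Participants will complete the MESA, UDI-6, IIQ-7, and FSFI questionnaires, and will then be randomized to an intervention group". The three quality-of-life scores therefore exist before allocation. They are collected again at week 4.
- **Secondary outcomes, quality of life:** "A change score will be calculated by subtracting the two scores".
- **Statistical Analysis** (the paragraph after Sample Size Estimate): "Continuous variables will be analyzed by students t-test and categorical variables will be analyzed by chi-square", with Fisher's exact test as the alternative for categorical data. The same paragraph adds: "A regression analysis will be performed for both continuous and discrete outcomes in order to simultaneously adjust for baseline demographics and characteristics". It gives no covariate list.
- **Randomization:** 1:1 allocation by "random permuted blocks of 4 and 6 stratified by institution".
- **Baseline Characteristics:** "this is a study of 150 people and so we have planned to include a regression analysis". This again names no covariate. (The 150 differs from the 138 in Sample Size Estimate, but that does not bear on this point.)
- **Sample Size Estimate**, on the secondary outcomes: "acknowledging that we may be underpowered to detect significant differences in these outcomes".

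The only ranking of analyses is intention-to-treat ahead of per-protocol for the primary outcome. That ranks analysis sets. It does not rank the simple test against the regression.

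**The concern.** No single sentence assigns the t-test to the change score. But the change score is the only form in which the three questionnaires are defined as outcomes, and the t-test is the only simple test named for continuous variables. Subtracting baseline fixes its coefficient at 1, whatever the true relation between the two measurements. A model that estimates the coefficient is, in large samples, never less precise and is often clearly better.

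Institution is built into the allocation but then disappears from the analysis. The regression might restore both terms. However, where the Outcome Measures section uses the same phrase for baseline covariates, it lists medical-record items (age, histories, menopausal status, hormonal therapy) and neither a questionnaire score nor institution.

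At stake is precision on Aim 2 outcomes that the plan already concedes may be underpowered, when the data that could recover part of it are being collected anyway. The plan also leaves open which of two p-values decides each outcome.

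**Working it through.** **1. The plan's own figure.** Inputs from Sample Size Estimate: 50% versus 25%, 80% power, alpha 5% (two-sided assumed), 20% dropout. With the unpooled formula, n per arm = (1.960 + 0.842)² × (0.50×0.50 + 0.25×0.75) / 0.25² = 54.94, so 55. Then 55/0.8 = 68.75, so 69 per arm and 138 in total. The stated figure is reproduced exactly and is not in dispute. About 55 per arm are evaluable, and that number is used below.

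**2. Change score against ANCOVA for the three scores.** Let rho be the correlation between baseline and week 4, and k the week-4 SD divided by the baseline SD. In units of the baseline variance:

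- variance of the change score: 1 + k² − 2·rho·k
- residual variance after adjustment for baseline: k²(1 − rho²)
- SE reduction: 1 − √[k²(1 − rho²) / (1 + k² − 2·rho·k)]

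Example, rho = 0.5 and k = 1: ratio 0.75/1.00 = 0.75, and 1 − √0.75 = 13.4%.

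The documents give neither rho nor k, so both are assumed over a range. Power is from simulation (40,000 runs, 55 per arm, two-sided 5%, true effect 0.5 baseline SD, ANCOVA with arm, baseline and institution). Equivalent n is the number per arm that a change-score analysis would need to match ANCOVA with 55.

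| rho | k | Variance ratio | SE reduction | Equivalent n | Power, change t-test | Power, ANCOVA |
|---|---|---|---|---|---|---|
| 0.3 | 0.7 | 0.417 | 35.4% | 132 | 71.0% | 97.3% |
| 0.3 | 1.0 | 0.650 | 19.4% | 85 | 59.1% | 77.2% |
| 0.3 | 1.3 | 0.805 | 10.3% | 68 | 46.5% | 54.6% |
| 0.5 | 0.7 | 0.465 | 31.8% | 118 | 83.3% | 98.9% |
| 0.5 | 1.0 | 0.750 | 13.4% | 73 | 73.7% | 84.5% |
| 0.5 | 1.3 | 0.912 | 4.5% | 60 | 59.4% | 63.1% |
| 0.7 | 0.7 | 0.490 | 30.0% | 112 | 95.3% | 99.9% |
| 0.7 | 1.0 | 0.850 | 7.8% | 65 | 91.5% | 94.9% |
| 0.7 | 1.3 | 0.991 | 0.5% | 56 | 79.8% | 79.8% |

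The k = 0.7 rows show the largest gains partly because 0.5 baseline SD is then 0.5/0.7 = 0.71 week-4 SD. Under the null, each test rejected in 4.8% to 5.1% of runs.

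**3. Institution in the primary test.** Simulation (200,000 runs) with 55 per arm, 50% versus 25% overall, two sites, and an assumed gap between sites in success rate. Power of the pooled chi-square, then of Cochran-Mantel-Haenszel (CMH) without continuity correction:

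| Site gap | Sites 28+27 per arm | Sites 41+14 per arm |
|---|---|---|
| 0 points | 78.9% / 78.3% | 78.9% / 78.2% |
| 10 points | 79.0% / 78.8% | 79.0% / 78.7% |
| 15 points | 79.2% / 79.6% | 79.3% / 79.4% |
| 25 points | 79.6% / 81.4% | 79.6% / 80.9% |

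The change is −0.7 to +0.4 points for gaps of 0 to 15 points, and +1.3 to +1.8 at 25. In a separate run with near-equal sites and no treatment effect, type I error was 5.3% (pooled) and 5.0% (CMH) with no site gap, and 4.1% and 5.0% at a 30-point gap. Ignoring the strata is therefore at worst slightly conservative when sites differ widely.

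**The case against.** **The regression may already cover this.** If its baseline covariates include the questionnaire score, the efficient analysis is already planned: regressing the change or the week-4 score on arm and baseline gives the same arm estimate and standard error. This stands in part. The precision loss then arises only if the t-test is taken as the main analysis. But the plan neither names the term nor says which analysis is main, so a reader cannot tell.

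**A ranking can be inferred for the primary outcome.** The 138 follows from an unadjusted two-proportion formula, and Baseline Characteristics presents the regression as a response to the trial's modest size. That suggests a supportive role for it. This is a fair inference for the primary outcome, but it does not extend to the three quality-of-life scores.

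**The institution term hardly matters for the primary outcome.** Correct on power. The reason to use it is to match the randomisation.

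Two stronger readings are tempting, and the documents support neither.

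- *A reader might infer that the plan inflates type I error.* Each named test alone holds about 5% or slightly less. In the null simulations, the chance that at least one of the change-score t-test and the ANCOVA fell below 0.05 was 5.4% to 8.5%. That figure needs a regression that already contains baseline and institution, which is not the reading behind the precision loss. It also needs the more favourable result to be the one reported. Nothing in the plan says that it will be, and the plan commits to CONSORT reporting and 95% confidence intervals.
- *A reader might infer that the ordered satisfaction, comfort and ease-of-use answers lose power through chi-square.* The plan does not say that they go to chi-square, and its regression for discrete outcomes could be ordinal. Nor is an ordered model uniformly better: for an assumed polarised effect (45/15/40 against even thirds), proportional odds had 7% power and chi-square 52%. That is a trade-off, so no change is recommended for those items.

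**Conclusion.** The point holds as a matter of efficiency and of naming the main analysis. It is not a matter of validity: the change-score t-test and the unstratified test are both sound under randomisation, and there is no bias.

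For UDI-6, IIQ-7 and FSFI, the gain from ANCOVA runs from almost nothing (0.5% of the standard error at rho 0.7, k 1.3) to large (35% at rho 0.3, k 0.7). The middle case, a 13% cut, is worth about 11 power points for a 0.5 SD effect. These sizes rest on assumed correlations, SD ratios and effect size. For the primary outcome the effect on power is close to nil unless the sites differ by clearly more than 15 points. The change is advisable but not essential to the trial's validity.

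**What to change.** State one main analysis per outcome, before any outcome data are seen by arm:

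1. **UDI-6, IIQ-7, FSFI:** ANCOVA of the week-4 score on arm, baseline score and institution.
2. **Primary outcome (PGI-I success):** Cochran-Mantel-Haenszel test without continuity correction, stratified by institution, to match the randomisation.
3. **Supportive:** the change-score t-test, the unstratified chi-square test, and the regression with further baseline covariates, which should be listed.

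Naming the main analysis in advance also removes any room to choose between two p-values.

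The cost is a few sentences of plan wording, with no new data, visits or participants. The downsides are about 0.6 to 0.7 points of primary power if sites do not differ, and almost no ANCOVA gain if week-4 scores are more spread than baseline and highly correlated with it.

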#### **Null hypotheses**

The null hypothesis for each outcome will be that there is no difference in the primary outcome between the continence pessary and Poise Impressa® groups.

## Baseline Characteristics

Baseline characteristics will be assessed using descriptive univariate analyses to characterize the total study population. Histograms will be generated to characterize the distribution of the specific outcome being assessed. The baseline characteristics of the two study arms will be analyzed using the Student's t test for continuous variables, and Chi-Square or Fisher's exact tests for categorical variables. Although a comparison of the baseline characteristics between study arms is not necessarily needed given the randomized design, this is a study of 150 people and so we have planned to include a regression analysis.

## Equivalence Testing

Our purpose is to compare the two treatment methods in regards to the primary outcome not to assess equivalence of these two therapies. We have calculated a sample size based on a clinically significant difference in the primary outcome such that if there is no a significant difference detected then we can conclude that a clinically significant change is not present.

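### A non-significant primary result is to be read as showing that no clinically significant difference exists, which a superiority test with 80% power cannot establish

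*Combined protocol and SAP*

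**What the plan says.** Under Sample Size Estimate the plan sets its target: "We aim to detect a clinically significant difference of 50% improvement with continence pessary versus 25% with the Poise Impressa". The stated basis is "Assuming an 80% power", a 5% alpha (sidedness not given) and "a 20% dropout rate", leading to 138 participants, 69 per group. The Null hypotheses section states a null of no difference between the groups. The main Statistical Analysis section names chi-square or Fisher's exact tests for categorical outcomes and adds: "A p-value of less than 0.05 will define statistical significance and 95% confidence intervals will be documented".

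The Equivalence Testing section says the trial is not meant to assess equivalence, then gives the only rule in the document for reading a null primary result: "if there is no a significant difference detected then we can conclude that a clinically significant change is not present". No equivalence or non-inferiority margin is defined, and nothing ties the confidence intervals to this conclusion.

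**The concern.** The section rejects equivalence testing and then draws an equivalence-type conclusion from non-significance alone. Failing to reject a null of no difference says only that zero is compatible with the data. Whether 25 points is also compatible depends on the confidence interval, which the rule does not consult. Power of 80% does not close the gap: it accepts that one trial in five will miss the planned difference when it is real.

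The trial is meant to help patients and providers choose between two devices. Under the rule, an inconclusive result, even one leaning clearly towards one device, would be presented as a firm negative. The plan warns of low power for the secondary outcomes only, so nothing tempers the conclusion for the primary one.

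**Working it through.** **Inputs.** From Sample Size Estimate: success rates of 50% and 25%, 80% power, 5% alpha, 20% dropout, 69 per group. From Randomization: 1:1 allocation. From Statistical Analysis: chi-square test, 95% intervals. Assumptions of this check: two-sided alpha; 55 analysed per arm (69 × 0.80 = 55.2) or, with no dropout, 69; a Poise Impressa success rate of 25% in all scenarios.

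**1. The plan's sample size.** With the unpooled normal approximation:

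n = (1.96 + 0.8416)² × (0.5×0.5 + 0.25×0.75) / 0.25² = 7.849 × 0.4375 / 0.0625 = 54.94, so 55 per arm.

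55 / 0.80 = 68.75, so 69 per arm and 138 in total. The stated figure reproduces exactly.

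**2. Precision of the difference.** At the average success rate of 37.5%, the 95% half-width is 1.96 × √(2 × 0.375 × 0.625 / n):

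- n = 55: 18.1 points
- n = 69: 16.2 points

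To a first approximation, an observed difference smaller than the half-width is non-significant, but the interval excludes 25 points only if the difference is below 25 − 18.1 = 6.9 points (n = 55) or 25 − 16.2 = 8.8 points (n = 69). Observed differences of roughly 7 to 18 points, or 9 to 16 points, are therefore non-significant and still compatible with 25. Counts near a 25% Poise Impressa rate agree: the largest differences whose Wald upper limit stays below 25 are 18/55 versus 14/55 (7.3 points, upper limit 24.2) and 23/69 versus 17/69 (8.7 points, upper limit 23.8).

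**3. Examples of results the rule would misread.**

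- 24/55 (43.6%) versus 15/55 (27.3%): difference 16.4 points. Pooled rate 39/110 = 0.3545; z = 0.1636 / √(0.3545 × 0.6455 × 2/55) = 1.79; p = 0.073. The Wald standard error is √(0.436×0.564/55 + 0.273×0.727/55) = 0.0899, giving a 95% interval of -1.3 to 34.0 points (Newcombe: -1.5 to 32.8).
- 27/69 versus 17/69: difference 14.5 points, p = 0.068, Wald interval -0.9 to 29.9.

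Neither excludes 25 points.

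**4. How often this happens.** All pairs of binomial outcomes were enumerated with the uncorrected chi-square test at two-sided 0.05. The last column is the share of non-significant trials whose Newcombe 95% interval still reaches 25 points in either direction.

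| True rates | n per arm | Non-significant | Of those, 25 points not excluded |
|---|---|---|---|
| 50% vs 25% | 55 | 21.1% | 85% |
| 50% vs 25% | 69 | 13.6% | 80% |
| 45% vs 25% | 55 | 38.9% | 76% |
| 45% vs 25% | 69 | 30.2% | 67% |
| 40% vs 25% | 55 | 60.1% | 63% |
| 40% vs 25% | 69 | 52.7% | 49% |
| 25% vs 25% | 55 | 95.0% | 21% |
| 25% vs 25% | 69 | 94.9% | 9% |

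With Wald intervals the last column is somewhat higher (for 40% vs 25%, 66% at n = 55 and 54% at n = 69).

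**The case against.** The strongest reply is that the sentence explains how the sample size was chosen and does not prescribe the wording of a report. The plan also promises 95% intervals and CONSORT 2010 presentation, so a reader could see the uncertainty. That makes harm less certain, but the document's only stated reading of a null result would then contradict the interval printed beside it.

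Two points of scale stand. First, where the truth is 40% versus 25%, the real difference is below the plan's 25 points, so the 60% non-significance rate there is not a rate of false conclusions; it shows how often the conclusion would be drawn, frequently without support. The rate of false conclusions at exactly 25 points is the ordinary type II error. Second, the analysis is intention-to-treat and the handling of missing data is left open, so 69 per arm is the favourable end of the range. Both sizes are shown above, and the problem is smaller at 69 but does not disappear.

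It is also true that some null results do exclude 25 points: about 79% of them at 55 per arm if both rates are 25%. The rule cannot tell these from the rest.

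Finally, the plan presents 25 points as the difference to detect, not as an equivalence margin, and does not say which estimate receives an interval. Both points bear on how the fix is written. Neither defends the sentence.

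**Conclusion.** The concern holds, and the sentence should be corrected before results are known because it governs the primary conclusion. If the difference is really 25 points, the rule yields a false statement of absence in about 21% of trials at 55 per arm, or about 14% at 69. Most of those null trials (85% and 80%) have intervals that still include 25 points. At smaller true differences a null result is more likely, and often leaves 25 points open.

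These figures rest on a two-sided 5% test, a 25% Poise Impressa success rate, the uncorrected chi-square test and Newcombe intervals. The logical error rests on none of them. The sample size calculation is sound for its own purpose.

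**What to change.** Replace the final sentence of Equivalence Testing with text such as:

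> If the primary comparison is not significant, the result will be reported as inconclusive unless the two-sided 95% confidence interval for the difference in success proportions lies wholly between -25 and +25 percentage points. Only then will a clinically significant difference be said to be excluded.

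State in Statistical Analysis that the primary result will be given as a difference in proportions with a 95% interval, and name the method (Newcombe, for example). The sponsor should confirm that 25 points is the difference it is content to call excluded. If it does not want to use 25 points in that way, deleting the sentence and reporting the estimate with its interval also removes the error.

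The cost is a sentence or two of text, with no new participants, visits or data. The one drawback is that some null results will have to be called inconclusive.
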